**(NCT03860662)**

**Study Protocol and Statistical Analysis Plan**

A total of 29 patients who developed spastic hemiplegia as a result of embolism or hemorrhage with Modified Ashworth Scale (MAS) phases of 2-4 and applied to Hatay Mustafa Kemal University, Faculty of Medicine, Physical Medicine and Rehabilitation polyclinic between the dates May 2018 – March 2019 were included in the study. Randomization was performed by generating random numbers as the Group 1 and Group 2. 15 patients were included in Group 1 to receive Botulinum toxin treatment, whereas 14 patients were included in Group 2 to receive Baclofen treatment.

Individuals who had received botulinum toxin injection treatment in the past 6 months, patients receiving oral antispastic treatment, individuals who have an allergy and hypersensitivity story related to the medication to be used, individuals who had diseases that might cause neuropathy and/or used medication and substances which might cause neuropathy in their medical history, individuals with hematoma, infections or skin lesions in the planned injection area, hemorrhage disorders, joint contracture and patients who were MAS grade were excluded from the study. Our study was regarded as positive and approved by decision 2018/159 of Hatay Mustafa Kemal University, Tayfur Ata Sökmen Faculty of Medicine, Clinical Researches Ethics Committee. Informed consent form was taken from all the participants of the study. The study was carried out in accordance with the Helsinki Declaration. The Clinical Trial number is NCT03860662.

The patients' gender, age, weight, height, cerebrovascular case etiology, symptom durations and hemiplegic sides were recorded. MAS was used to evaluate spasticity intensity. MAS grading is done as 1,1+,2,3,4 and it was graded successively as 1,2,3,4,5 to be able to do statistical analysis. The motor evaluation of the patients was performed using Brunnstrom motor staging (upper extremity, hand, lower extremity). A 10 cm. long Visual Analogue Scale (VAS) was used to evaluate the hemiplegic side pain of the patients. The daily life activities of the patients were evaluated with the Barthel index. The Barthel index consists of 10 questions and the highest total score that can be received is 100 (0-20 points: total dependency;

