21-61 points: severe dependency; 62-90 points: moderate dependency; 91-99 points: slight dependency; 100 points: total independence). The nociceptive flexor reflex (NFR) threshold value measurement was performed with electromyography on the unaffected lower extremities of the patients. The electrical stimulations were given with a bipolar stimulator from the sural nerve, near side of the lateral malleolus. In order to achieve a threshold value, the electrical stimulation was started from 0mA and increased in intervals (4mA intervals) until a NFR response was achieved. After the initial NFR response was achieved, the stimulation intensity was decreased in 2mA intervals until the response disappeared. Then, the stimulation intensity was arranged with high and low stimulations of 1mA until a stable NFR response was achieved. The stable NFR threshold value achieved in this manner was recorded. The electrical stimulation intensity which made it possible for the NFR threshold response to be achieved was recorded as mA unit. Prior to the treatment and on the 6th week which was the end of treatment, MAS, Brunnstrom stages, VAS values, Barthel daily life activities index and electromyographic NFR thresholds of all patients were recorded.

The 15 patients in the first group were injected onabotulinumtoxin A under ultrasonography guidance in their upper and lower extremity muscles which were 2 and over according to MAS, in suitable dosages according to the pre-determined dosage diagram (total dosage 100-300 IU). The 14 patients in the second group were given 5 mg of oral baclofen twice daily as the initial dosage starting from the first day. This was increased 5mg every 5 to 7 days up to 80mg until the effective antispasticity dosage was achieved (total dosage 30-80 mg). The dosage was not increased anymore since the patients were not able to tolerate higher dosages. Both patient groups were applied a physical therapy and rehabilitation program together with antispastic treatment. In the rehabilitation procedure, positioning, joint range of motion and stretching exercises, strengthening exercises, balance and coordination, ambulation exercises, hot or cold compress, functional electrical stimulation treatments were applied to each patient for 60 minutes. The treatment program was applied by the same physiotherapist for 6 weeks, 5 times a week and once each day.

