All obtained data were recorded with the Statistical Package Social Sciences (SPSS) version 21.0 statistical software. The control and analyses of the data were performed with the same software. In the statistical analyses, frequency (%) (median – minimum and maximum) was used for descriptive statistics. The mean and standard deviation values were expressed as ( $m \pm SD$ ). The data obtained through the measurements were evaluated separately each group with ShapiroWilk test in terms of normal distribution. In the comparison of values

which did not display normal distribution, nonparametric tests were used. While Mann-Whitney U test was used in the comparison of the two groups, Wilcoxon Signed Ranks test was used within the same group prior to and after comparisons. In the statistical analyses, p values lower than 0,05 were accepted as significant.

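### The only named between-group test ignores baseline, although every outcome has one; a baseline-adjusted rank comparison would be more efficient when baseline and week-6 values are moderately correlated

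*Combined protocol and SAP*

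**What the plan says.** The combined protocol and SAP has no numbered sections. These statements bear on the point.

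- **Design.** "A total of 29 patients who developed spastic hemiplegia" were included, 15 allocated to botulinum toxin and 14 to baclofen. "Randomization was performed by generating random numbers as the Group 1 and Group 2"; no stratification is mentioned.
- **Assessments.** "Prior to the treatment and on the 6th week which was the end of treatment, MAS, Brunnstrom stages, VAS values", the Barthel index and the NFR threshold were all recorded. Every outcome therefore has a baseline and a week-6 value.
- **Between groups.** "While Mann-Whitney U test was used in the comparison of the two groups". No covariate or adjusted model is named.
- **Within groups.** "Wilcoxon Signed Ranks test was used within the same group prior to and after comparisons". This is the only analysis in which baseline values are given a role.
- **When these tests apply.** "The data obtained through the measurements were evaluated separately each group with ShapiroWilk test", and for values "which did not display normal distribution, nonparametric tests were used". No test is named for values that pass the normality check.

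The statistical paragraph does not say whether the Mann-Whitney test takes week-6 values or changes from baseline. Its wording about measured data makes week-6 values the natural reading, but it is not explicit.

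**The concern.** The comparison of the two drugs is the only randomised contrast in the trial, and it rests on 29 patients. A baseline measurement of the same outcome is usually the best available predictor of the week-6 value. Leaving it out of the between-group test gives up precision that has already been paid for. With simple randomisation of so few patients, a chance baseline difference on some outcome is also quite possible, and an unadjusted comparison does not take account of it.

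The unstated input is a second, related problem. A test on week-6 values and a test on changes can disagree, so a reader cannot be sure which contrast a given p value belongs to.

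**Working it through.** The plan gives no power, effect size, SD or correlation, so there is no figure of its own to reproduce. The group sizes agree: 15 + 14 = 29.

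**Inputs from the documents:** 15 v 14; significance at 0.05; MAS recoded 1 to 5.

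**Assumptions:** two-sided test; true shift 0.8 SD; r from 0 to 0.8; equal SD at both visits for normal data. The ordinal case is a latent normal variable cut at 40/80% at baseline (3 levels) and at 15/40/70/90% at week 6 (5 levels).

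**Step 1: analytic check (normal data).** Variance relative to the week-6 comparison:
- changes: 2(1 − r) = 1.40 / 1.00 / 0.60 at r = 0.3 / 0.5 / 0.7;
- baseline-adjusted, with a small-sample penalty: (1 − r²)(1 + 1/25) = 1.04 / 1.00 / 0.95 / 0.78 / 0.53 at r = 0 / 0.2 / 0.3 / 0.5 / 0.7.

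Adjustment therefore breaks even at r of about 0.2.

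**Step 2: simulated power (%).** There were 40,000 trials per setting. Mann-Whitney (MW) is tie- and continuity-corrected. Rank ANCOVA regresses week-6 ranks on group and baseline ranks, with 26 df.

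| r | 0 | 0.2 | 0.3 | 0.5 | 0.7 | 0.8 |
|---|---|---|---|---|---|---|
| Normal: MW, week 6 | 51 | 51 | 50 | 51 | 51 | 51 |
| Normal: MW, change | 29 | 35 | 39 | 51 | 73 | 88 |
| Normal: rank ANCOVA | 51 | 53 | 54 | 62 | 76 | 87 |
| Ordinal: MW, week 6 | 49 | 49 | 49 | 49 | 49 | 49 |
| Ordinal: MW, change | 38 | 44 | 47 | 56 | 69 | 77 |
| Ordinal: rank ANCOVA | 50 | 51 | 52 | 58 | 68 | 77 |

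Gains below are taken before rounding, so they can differ by a point from the table.
- Over the week-6 test: 0–2 points at r = 0–0.2, 3–4 at 0.3, 8–11 at 0.5, 19–25 at 0.7.
- Over changes at r = 0.3 / 0.5 / 0.7: 16 / 11 / 3 (normal), 13 / 8 / 1 (mild skew, log-SD 0.5), 5 / 1 / −1 (ordinal). At r = 0.8 there is no gain.

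**Step 3: is the gain real?** Type I error is 4.5–4.8% for Mann-Whitney and 5.0–5.3% for rank ANCOVA, so a little of the gain reflects a conservative comparator. Without the continuity correction (20,000 trials, normal / ordinal), the gains over the week-6 test are:
- r = 0.3: 55.0 − 53.3 = 1.7 / 51.2 − 49.7 = 1.5;
- r = 0.5: 61.5 − 53.1 = 8.4 / 56.5 − 49.5 = 7.0;
- r = 0.7: 76.2 − 52.5 = 23.7 / 67.9 − 49.8 = 18.1;
- r = 0: a loss, 51.3 − 52.9 = −1.6 / 49.0 − 49.9 = −0.9.

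**Step 4: other effect sizes.** At 0.4 SD on normal data the gain over week 6 is about 2 / 4 / 10 points at r = 0.3 / 0.5 / 0.7. At 1.0 SD (no continuity correction) and r = 0.5 it is 80.3 − 71.7 = 8.6.

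**Step 5: unstated input.** With the 0.8 SD shift, the week-6 and change tests disagree on significance in 33 / 35 / 40% of trials (normal) and 21 / 22 / 27% (ordinal) at r = 0.3 / 0.5 / 0.7. If there were no effect and whichever test was significant were reported, the false-positive rate would be 8–9% (normal) or 7–7.5% (ordinal).

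**Step 6: chance imbalance.** The SE of the baseline difference is √(1/15 + 1/14) = 0.372 SD, so P(|difference| > 0.5 SD) = 0.178 per outcome. Given such an imbalance, no effect and normal data, false-positive rates at r = 0.3 / 0.5 / 0.7 are 7 / 11 / 16% (week 6), 13 / 11 / 8% (change) and 5 / 6 / 6% (rank ANCOVA). In the ordinal case the change test stays near nominal (6 / 5 / 5%).

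**The case against.** The strongest reply is that Mann-Whitney on a randomised comparison is conventional and valid, so adjustment is a preference and the only true documentary gap is the unstated input. Validity is granted. Even so, the preference has a measurable basis: across the range of r, rank ANCOVA is best or within about 2 points of best, while each unadjusted input does clearly worse somewhere.

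Several other objections stand as limits on the size.
- **Data type.** The largest gains over changes come from normal data, whereas the plan reserves these tests for non-normal values. The week-6 contrast is unaffected by a monotone transform, but the contrast with changes shrinks under skew and nearly vanishes for ordinal scales from r = 0.5.
- **Effect size.** 0.8 SD is favourable; at 0.4 SD the gains are roughly halved and power stays low with any of the tests.
- **Meaning of r.** In the ordinal rows r is the latent correlation. Latent 0.3 / 0.5 / 0.7 corresponds to about 0.26 / 0.43 / 0.61 between observed scores.
- **MAS entry.** Patients were enrolled "with Modified Ashworth Scale (MAS) phases of 2-4", which tends to lower r for MAS. With a more concentrated baseline (cuts at 80/97%, an assumption), gains over week 6 fall to about 2 / 5 / 10 points.
- **Conditional figures.** The imbalance rates apply only if an imbalance occurs, and none is documented. The 7–9% rate requires selective reporting, which nothing in the documents suggests.
- **Timing.** Enrolment ended in March 2019 and the text is in the past tense, so adjustment cannot now raise the power of the planned test.

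**Conclusion.** The point holds as a low-cost improvement; it is not an error in the plan. The named between-group test is valid but makes no use of baseline, and its input is not stated. Under the stated assumptions (15 v 14, 0.8 SD), and allowing for the continuity correction or its absence, rank ANCOVA gains about 2–4 points of power over a week-6 Mann-Whitney test at r = 0.3, 7–11 at 0.5 and 18–25 at 0.7. There is practically no gain at r of about 0.2 or less, and none over change scores at about 0.8. Confidence is medium, because r, the effect size and the ordinal cut-points are all assumed.

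**What to change.** For every outcome handled nonparametrically, name one baseline-adjusted between-group method: rank ANCOVA, with week-6 ranks regressed on treatment group and the baseline rank of the same outcome. Report Mann-Whitney beside it and state whether it uses week-6 values or changes; the authors know which was run, and one sentence settles it. If the adjusted analysis is added after the data were seen, label it post hoc and show it next to the planned test without replacing it.

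The cost is a change of wording and a short re-run on data already collected, with no new patients or visits. Adjustment spends one degree of freedom and may lose a point or two of power if baseline turns out not to predict week 6.

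### No primary outcome and no error control across five to seven measures, and a between-arm comparison that is loosely defined and ignores the recorded baseline

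*Combined protocol and SAP*

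**What the plan says.** The closing statistical paragraph of the combined protocol and SAP is the whole analysis plan. Each group's data are checked for normality with Shapiro-Wilk, and nonparametric tests are used for values that fail. Between arms, "Mann-Whitney U test was used in the comparison of the two groups". Within arms, "Wilcoxon Signed Ranks test was used within the same group prior to and after comparisons". One threshold covers everything: "In the statistical analyses, p values lower than 0,05 were accepted as significant".

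The outcomes come from the measurement paragraphs. Before treatment and at week 6, "MAS, Brunnstrom stages, VAS values, Barthel daily life activities index and electromyographic NFR thresholds of all patients were recorded". One of these has three parts: "Brunnstrom motor staging (upper extremity, hand, lower extremity". On numbers, "15 patients were included in Group 1 to receive Botulinum toxin treatment, whereas 14 patients were included in Group 2", allocated at random. On co-treatment, "Both patient groups were applied a physical therapy and rehabilitation program together with antispastic treatment".

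The available text does not state:
- a primary outcome, primary comparison or hypothesis;
- a multiplicity rule;
- whether the between-arm test uses week-6 values or change;
- any use of the baseline value in the between-arm comparison;
- which test applies to values that pass the normality check.

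**The concern.** The trial is randomised, so the comparison it supports is botulinum toxin against baclofen. The plan leaves that comparison open in three ways.

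1. Several measures each get their own test at 0.05 and none is ranked above the others. Any one significant result could be presented as the finding.
2. For each measure, at least two between-arm analyses fit the wording (week-6 values or change). They can give different answers, and nothing fixes the choice.
3. The baseline of every measure is recorded but not used to sharpen the comparison, which matters with 29 patients.

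The same threshold also covers the within-arm tests. If each measure receives all three tests, there are 5 × 3 = 15 p values (7 × 3 = 21), of which 10 (14) are within-arm. Both arms receive the same rehabilitation, so a within-arm p value reflects drug, rehabilitation and natural course together. It says nothing about one drug against the other.

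**Working it through.** **Inputs from the document.** Arms of 15 and 14; threshold 0.05; five measures, or seven if the Brunnstrom upper extremity, hand and lower extremity stages are counted separately; two time points. The plan gives no power calculation, effect size, SD or correlation, so it has no figure of its own to reproduce.

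**Assumptions.** Two-sided tests; normal data unless stated; baseline to week-6 correlation ρ from 0.3 to 0.8; a true difference of 0 or 0.8 SD of the outcome.

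**1. Several measures, no primary.** For 15 versus 14, the largest two-sided rejection region of the exact Mann-Whitney test below 0.05 is U ≤ 59 in either direction, with true level 0.0459. For k independent measures with no true difference, P(at least one false positive) = 1 − (1 − 0.0459)^k:
- k = 5: 1 − 0.9541^5 = 0.209, about 21%.
- k = 7: 1 − 0.9541^7 = 0.280, about 28%.

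Simulation with equal correlation 0.7 between measures gives about 15% (five) and 18% (seven).

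**2. Week-6 values or change.** With no true difference, each Mann-Whitney version alone rejects in about 4.6% of trials. Reporting whichever version is significant rejects in 8.1%, 8.6%, 8.7% and 8.7% at ρ = 0.3, 0.5, 0.7 and 0.8, that is 8–9%.

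**3. Precision lost by not adjusting.** With outcome SD 1 at both times, the SD of change is √(2(1 − ρ)) and the residual SD after baseline adjustment is √(1 − ρ²). A 0.8 SD difference is therefore worth 0.8/√(2(1 − ρ)) on change and 0.8/√(1 − ρ²) with ANCOVA. The power columns are simulated.

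| ρ | Effect, week 6 | Effect, change | Effect, ANCOVA | Power, MW week 6 | Power, MW change | Power, ANCOVA |
|---|---|---|---|---|---|---|
| 0.3 | 0.80 | 0.68 | 0.84 | 51% | 39% | 57% |
| 0.5 | 0.80 | 0.80 | 0.92 | 51% | 51% | 65% |
| 0.7 | 0.80 | 1.03 | 1.12 | 51% | 73% | 81% |
| 0.8 | 0.80 | 1.26 | 1.33 | 51% | 88% | 92% |

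Repeat runs differ by about one percentage point, so the ranges are quoted as 39–89% for change and 57–93% for ANCOVA. All three hold type I error near 5% (ANCOVA 4.9–5.2%).

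MAS and Brunnstrom are ordinal. On simulated five-level data, a rank-based ANCOVA gives 53–82% power, against about 50% for Mann-Whitney on week-6 values and 36–78% on change. The gain is smaller, and it depends on the assumed category cut-points.

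**4. Why within-arm p values should not be compared (illustration only).** Give both arms the same true change of 0.5 SD of the change score. The signed-rank test is then significant in about 42% of trials at n = 15 and 41% at n = 14. Exactly one arm is significant in 0.42 × 0.59 + 0.41 × 0.58 = 0.49, about half of trials, although the drugs do not differ. The rate is about 50% at 0.6 SD and falls to 9% at 0 and 13% at 1.0 SD. For tied ordinal changes it runs from under 0.1% to 49%, so it cannot be sized for MAS or Brunnstrom.

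**The case against.** The strongest reply is that the plan does name a between-arm test, that an unadjusted Mann-Whitney test is valid in a randomised trial, and that before-after tests beside it are ordinary. All of that stands. A reader might infer that the sponsor means to judge the drugs by which arm improves significantly. The text does not say so, and the roughly 50% one-arm-only rate misleads only someone who sets the between-arm test aside. It shows why within-arm tests should carry no drug claim; it does not measure an error in the plan.

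Second, the named tests apply only to non-normal values. Normal samples of this size would pass Shapiro-Wilk in both arms about 0.95 × 0.95 = 90% of the time, so figures from normal data describe tests that the plan's own rule would often not use. That limits the precision of the figures. It does not rescue the plan, which names no test for values that pass, and several measures tested at 0.05 accumulate error whichever test is used.

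Third, the wording speaks of measured values and never defines a change score, so week-6 values are the more natural reading. This makes a free choice less likely, but the text does not settle it.

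Fourth, the multiplicity figures treat all measures as continuous, although MAS and the Brunnstrom stages are ordinal. They are approximate for that reason too.

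Finally, part of the document was removed before publication or review, so the statement that no primary is named covers the available text only.

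**Conclusion.** The concern holds as a gap in definition and error control and as precision given up, not as bias. Across the between-arm tests, the chance of at least one false positive is about 15–28%, depending on whether there are five or seven measures and on their correlation (0 to 0.7). An open choice of variable would take the error per measure from about 4.6% to 8–9%. At a 0.8 SD difference, baseline adjustment gives 57–93% power, against about 51% on week-6 values and 39–89% on change. The gain over change scores is small when ρ is high, and the gain is smaller on ordinal scales. All of this rests on assumed effects, correlations and mostly normal data, because the documents supply none.

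Two stronger readings are not supported: that the between-arm test is missing or invalid, and that within-arm results are the planned basis for comparing the drugs. The point should be fixed because it governs how every result is read and the repair uses data already collected.

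**What to change.** 1. Base every botulinum toxin versus baclofen claim on the between-arm comparison of week-6 values adjusted for the same measure's baseline: ANCOVA, or a rank-based or ordinal version for MAS and Brunnstrom. Report an estimate with 95% CI. State that this analysis replaces the choice by normality test.
2. Have the sponsor name one of the measures already collected as primary and treat the rest as secondary. The documents do not rank them, so the choice is the sponsor's. With one primary test, the confirmatory error is 5%.
3. The text is in the past tense with final group sizes. If data have been seen, label both the adjusted analysis and the primary as post hoc. Then either adjust across the between-arm tests (Bonferroni: 0.05/5 = 0.01 or 0.05/7 = 0.0071) or call them all exploratory. A primary chosen late does not remove the 15–28% risk.
4. Report within-arm change descriptively with 95% CI, labelled as change under drug plus rehabilitation and not as evidence comparing the drugs.

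The cost is one adjusted model per measure, some wording, and giving up within-arm significance statements. No new data are needed.

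### The plan names only a Mann-Whitney p value for comparing the two treatments, with no between-group estimate, confidence interval or stated use of baseline

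*Combined protocol and SAP*

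**What the plan says.** The statistical methods are in the closing paragraphs of the combined protocol and SAP, under its single heading, Study Protocol and Statistical Analysis Plan.

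- **Distribution check:** "The data obtained through the measurements were evaluated separately each group with ShapiroWilk test in terms of normal distribution". Nonparametric tests are then tied to values that fail this check. No test is named for values that pass it.
- **Between groups:** "While Mann-Whitney U test was used in the comparison of the two groups". No other two-group method appears.
- **Within groups:** the Wilcoxon signed ranks test, before against after.
- **Descriptives:** frequencies, and medians with minimum and maximum. For means, "The mean and standard deviation values were expressed as" m ± SD. The text does not say that these are given by arm.
- **Decision rule:** "In the statistical analyses, p values lower than 0,05 were accepted as significant".

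The earlier paragraphs show that baseline was collected: "Prior to the treatment and on the 6th week which was the end of treatment, MAS, Brunnstrom stages, VAS values", together with the Barthel index and the NFR threshold, were recorded. Motor function is assessed by "Brunnstrom motor staging (upper extremity, hand, lower extremity"). The MAS grades were recoded: "it was graded successively as 1,2,3,4,5 to be able to do statistical analysis". No part of the document mentions a between-group difference, an effect size or a confidence interval.

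**The concern.** The trial compares two active treatments in 29 patients. A reader needs to know how large the difference between them is and how well it has been measured. A p value compared with 0.05 gives neither. At this size a non-significant result is compatible with large differences in either direction, and a significant one with anything from almost nothing to a very large effect.

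The second gap is the input to the between-group test. Week-6 values, changes from baseline and baseline-adjusted values can differ considerably in precision, and which is best depends on how strongly baseline predicts week 6. Leaving the choice unstated allows it to be made after the data are seen. It also leaves a chance baseline imbalance uncorrected if only week-6 values are compared.

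**Working it through.** The plan gives no sample-size calculation, SD or target difference, so there is no figure of its own to reproduce beyond 15 + 14 = 29, which agrees. The steps below show what an interval would convey.

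**Inputs.** Group sizes 15 and 14, and the 0.05 threshold, come from the document. Two-sidedness, approximate normality, a common SD and all correlations r between baseline and week 6 are assumptions. Results are in SD units of the outcome.

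**1. Unadjusted week-6 difference**
- SE = √(1/15 + 1/14) = 0.3716 SD
- t(0.975, 27 df) = 2.052
- Half-width = 2.052 × 0.3716 = 0.762 SD

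An observed difference of zero therefore leaves about −0.76 to +0.76 SD open. An observed difference of 0.762 SD, just significant by a t test, has an interval from 0 to about 1.52 SD.

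**2. Baseline-adjusted difference (ANCOVA)**
- Approximate half-width = t(0.975, 26 df) × 0.3716 × √(1 − r²)
- Simulating the model at 15 versus 14 (40,000 runs) adds the small cost of chance baseline imbalance; coverage was 95%.

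| Assumed r | Formula | Simulated mean |
|---|---|---|
| 0 | 0.76 | 0.771 |
| 0.3 | 0.729 | 0.735 |
| 0.5 | 0.662 | 0.669 |
| 0.7 | 0.546 | 0.550 |

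**3. Change from baseline**
- Half-width = 0.762 × √(2(1 − r)), giving 0.90, 0.76 and 0.59 SD at r = 0.3, 0.5 and 0.7.
- A Hodges-Lehmann interval on change has a simulated half-width of 0.79 SD of the change. In outcome SDs this is 0.79 × √1.4 = 0.93 at r = 0.3 and 0.79 × 1 = 0.79 at r = 0.5. Both are wider than the unadjusted 0.76.

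**4. Does the unstated choice matter?** Approximate power for a true 0.8 SD difference (normal approximation for means):

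| Assumed r | Week 6 only | Change | ANCOVA |
|---|---|---|---|
| 0.3 | 58% | 44% | 62% |
| 0.7 | 58% | 79% | 85% |

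The probability of a chance baseline imbalance above 0.5 SD is 2 × [1 − Φ(0.5/0.3716)], about 18%.

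**5. Ordinal outcomes**
- For the probability of superiority near 0.5 without ties, half-width = 1.96 × √(30/(12 × 15 × 14)) = 0.214, so roughly 0.29 to 0.71.
- Simulation with ties, over a range of assumed grade distributions, gave about 0.18 to 0.22, and about 0.16 when 80% of patients share one grade.

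**6. Number of intervals.** MAS 1 + Brunnstrom 3 + VAS 1 + Barthel 1 + NFR 1 = 7. This counts MAS once; the document does not say how many MAS values per patient are analysed.

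**The case against.** Several points on the other side have force.

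- **A reader may be able to recover an interval.** Means and SDs are among the listed summaries and the group sizes are known. If the summaries are given by arm, a rough unadjusted week-6 interval can be rebuilt for the continuous outcomes. This stands, so it would be too strong to infer that size and precision are lost altogether. By-arm reporting is not stated, however. A baseline-adjusted interval also cannot be rebuilt from separate before and after summaries, and medians with ranges do not yield a probability of superiority.
- **Mann-Whitney is conditional.** A reader might infer that it applies to every outcome. The text ties nonparametric tests to non-normal values, so a parametric test may be implied elsewhere. None is named, and a t test p value alone would leave the same gap.
- **Baseline is used.** It enters the within-group Wilcoxon tests. Those tests do not estimate the difference between treatments, and the point is confined to the between-group comparison.
- **The SD figures assume normality.** They illustrate precision; a just-significant t test is not a just-significant Mann-Whitney result. This stands as a limit on the figures, but the omission does not depend on them.
- **Ties may be fewer than entry suggests.** Entry was limited to "Modified Ashworth Scale (MAS) phases of 2-4", which compresses MAS at baseline but not necessarily at week 6. This is why a range is given for the ordinal outcomes.
- **The document is written in the past tense.** The request is therefore probably about reporting rather than a prospective plan. That affects how added analyses are labelled, not whether they are useful.

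**Conclusion.** The point holds in this form: the plan names a single, conditional between-group test judged by its p value, leaves its input unspecified, and plans no between-group estimate, confidence interval or baseline adjustment, although the baseline values were collected.

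The omission itself rests on the text alone. The size rests on the stated assumptions. Under them, the adjusted half-width is about 0.73, 0.67 or 0.55 SD at correlations of 0.3, 0.5 or 0.7, against 0.76 SD unadjusted. At zero correlation adjustment gains nothing (about 0.77 SD). The document gives no correlations.

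A reader might also infer that the trial means to claim similar efficacy from a non-significant test. The document makes no such claim, and the point does not need one. This is an improvement that should be made. It does not invalidate the named tests.

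**What to change.** Fix one measure per outcome and report each with a 95% confidence interval.

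- **NFR threshold (mA), VAS (cm) and Barthel (points):** the week-6 between-group mean difference adjusted for the baseline value by ANCOVA, in natural units. If residuals are skewed, check the same estimate with a bootstrap or permutation interval. Do not switch to change scores, which can be less precise than no adjustment when the correlation is low.
- **MAS and each of the three Brunnstrom components:** the probability of superiority at week 6, with ties counted as one half, alongside the Mann-Whitney test. This measure makes no baseline adjustment, but it avoids treating a one-grade change as equivalent across an ordinal scale.

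State that the Mann-Whitney test for these ordinal outcomes uses week-6 values. Base conclusions on the intervals, and do not read p ≥ 0.05 as showing no difference. State that the intervals, at least seven, are not adjusted for multiplicity. Label them as not prespecified if the data have already been analysed.

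The cost is a little more analysis work on data already recorded, and intervals that will be visibly wide.
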